1 SYNOPSIS

Title: A Phase 2 Study to Investigate the Safety and Efficacy of ABBV-105 Given Alone or in Combination with Upadacitinib (ABBV-599 Combination) with a Background of Conventional Synthetic DMARDs in Subjects with Active Rheumatoid Arthritis with Inadequate Response or Intolerance to Biologic DMARDs

μ	
Background and Rationale:	ABBV-105 is a novel, covalent Bruton's tyrosine kinase (Btk) inhibitor being developed for the treatment of immune-mediated inflammatory diseases including rheumatoid arthritis (RA).
	types associated with the pathogenesis of RA and other autoimmune diseases. Btk is required for the propagation of pro-inflammatory signals downstream of immunoreceptors that promote autoimmune disease pathogenesis. Compared to other Btk inhibitors, CC-292 (Celgene) and ibrutinib (Pharmacyclics/Janssen), ABBV-105 showed better potency, superior selectivity, and less off-target activity which is considered favorable for administration in humans.
	Upadacitinib (ABT-494) is a novel Janus kinase (JAK) inhibitor, which displays unique selectivity for the JAK1 receptor which is currently being developed for the treatment of adult patients with moderately to severely active rheumatoid arthritis (RA; Phase 3), psoriatic arthritis (Phase 3), atopic dermatitis (Phase 3), Crohn's disease (Phase 3), ulcerative colitis (Phase 2), and axial spondyloarthritis (Phase 2). As of 20 June 2017, a total of 1232 subjects have received upadacitinib, which includes 469 healthy volunteers, 553 rheumatoid arthritis (RA) patients, and 210 Crohn's disease patients. Upadacitinib was generally well-tolerated and the types of adverse events (AEs) seen were typical of patients treated with immunosuppressant therapies.
	ABBV-105 and upadacitinib given alone or in combination with each other (as the ABBV-599 combination therapy) should be effective in decreasing signs and symptoms associated with active RA in patients with inadequate response or intolerance to biologic disease-modifying anti-rheumatic drugs (bDMARDs) by interfering with the JAK1/Btk pathways. Concurrent inhibition of JAK1/Btk pathways in RA may increase percent of those responding as well as depth of response, while maintaining an acceptable safety profile.
Objective and Endpoint(s):	The main objective of this dose-exploratory study is to evaluate the safety and efficacy of ABBV-105 and ABBV-599 (ABBV-105 plus upadacitinib) vs placebo on a background of conventional synthetic disease-modifying anti-rheumatic drugs (csDMARDs) for the treatment of signs and symptoms of RA at 12 weeks in bDMARD-inadequate response (bDMARD-IR) or bDMARD-intolerant subjects with moderately to severely active RA and to define optimal dose(s) for further development.
	Primary Endpoint:
	 Change from baseline in disease activity score (DAS)28 (C-reactive protein [CRP]) at Week 12.

	Secondary Endpoints:
	2. Change from baseline in clinical disease activity index (CDAI) and simplified disease activity index (SDAI) at all visits;
	 Proportion of subjects achieving Clinical Remission (CR) at Week 12. CR is defined as DAS28 CRP < 2.6;
	 Proportion of subjects achieving low disease activity (LDA) at Week 12. LDA is defined as DAS28 CRP ≤ 3.2;
	 Proportion of subjects achieving LDA or CR based on CDAI criteria at all visits;
	6. ACR20/50/70 response rates at all visits;
	 a. ACR20/50/70 response rate will be determined based on 20%/50%/70% or greater improvement in Tender Joint Count (TJC) and Swollen Joint Count (SJC) and ≥ 3 of the 5 measures of Patient's Assessment of Pain (Visual Analog Scale [VAS]), Patient's Global Assessment of Disease Activity (PtGA), Physician's Global Assessment of Disease Activity (PhGA), Health Assessment Questionnaire Disability Index (HAQ-DI), or high-sensitivity C-reactive protein (hsCRP);
	 Change from baseline in individual components of ACR response at all visits;
	 Change from baseline in DAS28(CRP) and DAS28 (erythrocyte sedimentation rate [ESR]) at all visits;
	9. Change from baseline in morning stiffness at all visits;
	10. Change from baseline in HAQ-DI at all visits;
	 Proportion of subjects achieving minimal clinically important difference (MCID) in change from baseline in HAQ-DI (defined as change from baseline in HAQ-DI ≤ -0.3) at all visits;
	 Proportion of subjects achieving American College of Rheumatology (ACR)/ European League Against Rheumatism (EULAR) Boolean remission at all visits.
Investigator(s):	Multicenter
Study Site(s):	Approximately 125 sites worldwide
Study Population and Number of Subjects to be Enrolled:	Approximately 240 male and female adult subjects who are at least 18 years of age with a diagnosis of RA for \geq 3 months and also fulfill the 2010 ACR/EULAR classification criteria for RA. Subjects have been treated for \geq 3 months with \geq one bDMARD but continue to exhibit active RA or had to discontinue bDMARD(s) due to intolerability or toxicity, irrespective of treatment duration.
Investigational Plan:	This is a 12-week, randomized, double-blind, parallel-group, Phase 2, multicenter study designed to assess the safety and efficacy of ABBV-105, upadacitinib, and ABBV-599 (ABBV-105 plus upadacitinib) in subjects with active RA who have had inadequate response to bDMARD therapy and are on stable background csDMARD treatment. An upadacitinib reference arm is included in the study design to aid with interpretation of ABBV-599 efficacy. The study duration will include a 35-day maximum screening period; a 12-week randomized,

	double blind, parallel-group treatment period with 30-day follow-up. Study visits will be conducted at Screening, Baseline, Week 2, Week 4, Week 8, and Week 12.
Key Eligibility Criteria:	 Adult male or female, at least 18 years old. Diagnosis of RA for ≥ 3 months based on the 2010 ACR/EULAR classification criteria for RA.
	 Subject meets the following minimum disease activity criteria: ≥ 6 swollen joints (based on 66 joint counts) and ≥ 6 tender joints (based on 68 joint counts) at Screening and Baseline Visits; and hsCRP ≥ 3 mg/L (central lab) at Screening Visit. Subjects must have been treated for ≥ 3 months with ≥ 1 bDMARD therapy but continue to exhibit active RA or had to discontinue due
	 Subjects must have been receiving csDMARD therapy ≥ 3 months and on a stable dose for ≥ 4 weeks prior to the first dose of study drug.
	 The following csDMARDs are allowed (stable dose for ≥ 4 weeks prior to the first dose of study drug): oral or parenteral methotrexate (MTX) (7.5 to 25 mg/week), sulfasalazine (≤ 3000 mg/day), hydroxychloroquine (≤ 400 mg/day), chloroquine (≤ 250 mg/day), and leflunomide (≤ 20 mg/day).
	 A combination of up to two background csDMARDs is allowed EXCEPT the combination of MTX and leflunomide. Subjects must have discontinued all bDMARDs prior to the first dose of study drug. The washout period for bDMARDs prior to the first dose of study drug is specified below or should be at least
	 five times the mean terminal elimination half-life of a drug: ≥ 4 weeks for etanercept, adalimumab, infliximab, certolizumab, golimumab, tocilizumab, and abatacept; ≥ 1 year for rituximab OR ≥ 6 months if B cells have returned to pretreatment level or normal reference range (central lab) if pretreatment levels are not available (TBNKM cell testing may be completed at Screening rather than Baseline if B cell testing is indicated)
	 Subject must not have prior exposure to any JAK inhibitor for greater than 2 weeks (including but not limited to upadacitinib, tofacitinib, baricitinib, and filgotinib). A washout period of ≥ 30 days is required for any JAK inhibitor prior to the first dose of study drug.
Study Drug and Duration of Treatment:	Study drug will be taken orally as ABBV-105 and/or matching placebo capsules and upadacitinib and/or matching placebo tablet once daily with or without food.
	totaling doses of 5 mg, 20 mg, or 60 mg once daily (QD) and 1 tablet of

	capsules of ABBV-105 totaling a dose of 60 mg combined with 1 oral tablet of upadacitinib 15 mg QD. The upadacitinib arm will be administered 3 capsules ABBV-105 placebo and 1 oral tablet of upadacitinib 15 mg QD. Approximately 240 subjects who meet eligibility criteria will be randomized in a 3:2:2:2:2:1 ratio to 1 of 6 treatment groups: • ABBV-105 60 mg and upadacitinib 15 mg QD (n = 60)	
	 ABBV-105 60 mg and upadacitinib 15 mg QD (n = 60) 	
	 ABBV-105 60 mg and upadacitinib placebo QD (n = 40) 	
	 ABBV-105 20 mg and upadacitinib placebo QD (n = 40) 	
	 ABBV-105 5 mg and upadacitinib placebo QD (n = 40) 	
	 ABBV-105 placebo and upadactinib 15 mg QD (n = 40) 	
	 ABBV-105 placebo and upadacitinib placebo QD (n = 20) 	
Date of Protocol Synopsis:	15 October 2019	

2 INTRODUCTION

2.1 Background and Rationale

Why Is This Study Being Conducted

ABBV-105 is a novel, covalent Bruton's tyrosine kinase (Btk) inhibitor being developed for the treatment of immune-mediated inflammatory diseases including rheumatoid arthritis (RA).

Btk is a non-receptor tyrosine kinase expressed in multiple immune cell types associated with the pathogenesis of RA and other autoimmune diseases. Btk is required for the propagation of proinflammatory signals downstream of immunoreceptors that promote autoimmune disease pathogenesis. Compared to other Btk inhibitors, CC-292 (Celgene) and ibrutinib (Pharmacyclics/Janssen), ABBV-105 showed better potency, superior selectivity, and less off-target activity which is considered favorable for administration in humans.

The hematopoietic expression and signaling function of Btk downstream of numerous receptors has raised interest in pharmacologic targeting of Btk for immune-mediated inflammatory diseases including RA.¹ The potential clinical value of Btk inhibition has been supported by studies in preclinical models of arthritis and lupus.^{2,3} These have demonstrated: 1) complete abrogation of arthritis in the collagen-induced arthritis model when initiated at disease onset, consistent with the effect of Btk inhibition on autoantibody production,^{2,3} 2) efficacy in myeloid-mediated animal arthritis models, consistent with the effects of Btk inhibition on macrophage, mast cell, dendritic cell, and neutrophil activity,^{2,3} and 3) marked reductions of proteinuria in mouse models of lupus, consistent with the effect of Btk inhibition on autoantibody production and/or myeloid cell activation.⁴⁻⁶

Upadacitinib is a novel Janus kinase (JAK) inhibitor, which displays unique selectivity for the JAK1 receptor which is currently being developed for the treatment of adult patients with moderately to severely active RA (Phase 3), psoriatic arthritis (Phase 3), atopic dermatitis (Phase 3), Crohn's disease (Phase 3), ulcerative colitis (Phase 2), and axial spondyloarthritis (Phase 2). As of 20 June 2017, a total of 1232 subjects have received upadacitinib, which includes 469 healthy volunteers, 553 RA patients, and 210 Crohn's disease patients. Upadacitinib was generally well-tolerated, and the types of adverse events (AEs) seen were typical of patients treated with immunosuppressant therapies.

Clinical Hypothesis

ABBV-105 given alone or in combination with upadacitinib (as the ABBV-599 combination therapy) should be effective in decreasing signs and symptoms associated with active RA in patients with inadequate response or intolerance to biologic disease-modifying anti-rheumatic drugs (bDMARDs) by interfering with the JAK1/Btk pathways. Concurrent inhibition of JAK1/Btk pathways in RA may increase percent of those responding as well as depth of response (relative to inhibiting either pathway alone), while maintaining an acceptable safety profile.

2.2 Benefits and Risks to Subjects

Preclinical toxicology studies of ABBV-105 in animals and ex vivo human samples suggest that the potential risks to human subjects of ABBV-105 treatment are anemia, bleeding associated with platelet dysfunction, and lymphopenia. Reductions in lymphocytes and the known mechanism of action suggest the potential for an increased susceptibility to infection.

In Phase 1 Studies M16-356 (single doses of ABBV-105 ranging from 2 to 125 mg), M16-357 (multiple doses of ABBV-105 ranging from 3 - 60 mg), and M16-044 (co-administration of upadacitinib 30 mg with ABBV-105 ranging from 10 - 60 mg), ABBV-105 alone or ABBV-105 co-administration with upadacitinib was well-tolerated with no serious adverse events (SAEs) observed in healthy adult subjects.

Taken together, the safety data from the Phase 1 program support further development of ABBV-105 given alone or in combination with upadacitinib (ABBV-599) in Phase 2 in subjects with RA.

For safety monitoring, the following are included in the protocol:

- Exclusion of subjects with chronic or recent infections;
- Screen subjects for tuberculosis (TB); exclude patients with active TB or latent TB without
 history of appropriate prophylaxis: latent TB as assessed by Interferon Gamma Release Assay
 (IGRA) QuantiFERON Tuberculosis (TB) Gold in Tube Test or equivalent (i.e., or T SPOT.*TB* test; as
 available and if compliant with local TB guidelines) and/or a purified protein derivative (PPD)
 test (or both if required per local guidelines).
- Subjects will also be screened for human immunodeficiency virus (HIV) and hepatitis B and C.
- If a subject develops a serious infection or opportunistic infection with study treatment, study drug should be interrupted and appropriate treatment of the infection should be initiated.
- Review SAEs of infection on a real time basis and query for additional information as clinically indicated
- A supplemental herpes zoster form will be used to collect additional information for any herpes zoster infections.

See Section 3.4 for information on the Data Monitoring Committee (DMC).

For further details, please see findings from completed studies, including safety data in the ABBV-105 and upadacitinib Investigator's Brochures.^{7,8}

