Important Medical Event Requiring Medical or Surgical Intervention to Prevent Serious Outcome An important medical event that may not be immediately lifethreatening or result in death or hospitalization, but based on medical judgment may jeopardize the subject and may require medical or surgical intervention to prevent any of the outcomes listed above (i.e., death of subject, life threatening, hospitalization, prolongation of hospitalization, congenital anomaly, or persistent or significant disability/incapacity). Additionally, any elective or spontaneous abortion or stillbirth is considered an important medical event. Examples of such events include allergic bronchospasm requiring intensive treatment in an emergency room or at home, blood dyscrasias or convulsions that do not result in inpatient hospitalization, or the development of drug dependency or drug abuse.

All AEs reported from the time of study drug administration until 30 days after discontinuation of study drug administration will be collected, whether solicited or spontaneously reported by the subject. In addition, SAEs and protocol-related nonserious AEs will be collected from the time the subject signs the study-specific informed consent.

AbbVie will be responsible for Suspected Unexpected Serious Adverse Reactions (SUSAR) reporting for the Investigational Medicinal Product (IMP) in accordance with global and local requirements.

AEs will be monitored throughout the study to identify any of special interest that may indicate a trend or risk to subjects.

Adverse Events of Special Interest

The following adverse events of special interest (AESI) will be monitored during the study:

- Serious infections
- Opportunistic infections
- Herpes zoster
- Tuberculosis
- Malignancy (all types)
- Gastrointestinal perforations
- Adjudicated cardiovascular events (e.g., major adverse cardiovascular event [MACE])
- Anemia
- Neutropenia
- Lymphopenia
- Increased serum creatinine and renal dysfunction
- Hepatic events and increased hepatic transaminases
- Elevated creatine phosphokinase (CPK)

• Embolic and thrombotic events (non-cardiac, non-CNS).

Adverse Event Severity and Relationship to Study Drug

The investigator will classify AEs according to the Rheumatology Common Toxicity Criteria v.2.0 (Appendix F).

If no grading criteria are provided for the reported event, then the event should be as follows:

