### 9.2.2 Adverse Event Overview

An overview of AEs will be presented consisting of the number and percentage of subjects experiencing at least one event for each of the following AE categories:

- All TEAEs
- Treatment-emergent serious adverse events (SAEs)
- Treatment-emergent severe adverse events
- TEAEs reasonably possibly related to study drug
- TEAEs of special interest (AESIs)
- TEAEs leading to discontinuation of study drug
- TEAE leading to death
- All deaths

Additional AEs may be considered for tabulation/summary based on recommendations from Clinical and Safety as deemed appropriate.

For AESIs, the point estimate and 95% CI (using normal approximation) will be provided for the treatment difference in AE percentages.

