## 9.2.3 Treatment-Emergent Adverse Events by SOC and/or PT

The number and percentage of subjects experiencing adverse events will be tabulated by SOC and MedDRA PT by "as treated" treatment groups and overall. The SOCs will be presented in alphabetical order, and the PTs will be presented in alphabetical order within each SOC.

The following summaries of adverse events will be generated:

- All TEAEs
- Treatment-emergent serious adverse events (SAEs)
- Treatment-emergent severe adverse events
- TEAEs reasonably possibly related to study drug
- TEAEs leading to discontinuation of study drug
- TEAE leading to death
- Frequent AEs (reported in 2% of subjects or more in any treatment group)

Subjects reporting more than one adverse event for a given MedDRA preferred term will be counted only once for that term (most severe incident for the severity tables and most related incident for the relationship tables). Subjects reporting more than one type of adverse event within a SOC will be counted only once for that SOC. Subjects reporting more than one type of adverse event will be counted only once in the overall total. In addition, if the same adverse event occurs multiple times within a subject, the highest severity and level of relationship to investigational product will be reported. In addition, TEAEs will be summarized by PT and sorted by decreasing frequency for the total active group.

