## Appendix B. Definition of Adverse Events of Special Interest

Adverse Events of Special Interest (AESI) will be identified using the following search criteria:

AESI	Type of MedDRA Query	Broad or Narrow Search	SMQ/CMQ Search Criteria
Serious Infections	CMQ		"Infections" – Subset for SAEs
Opportunistic Infection	CMQ		"Opportunistic Infection"
Possible Malignancy	SMQ	Narrow	"Malignancies"
Malignancy	SMQ		"Malignant tumours"
Non-Melanoma Skin Cancer (NMSC)	SMQ	Broad	Skin Malignant tumours (Broad SMQ) removing Melanoma CMQ
Malignancy excluding NMSC			"Malignant tumours" SMQ removing NMSC output
Lymphoma	SMQ		"Malignant Lymphomas"
Hepatic Disorder (Hepatic Events and Increased Hepatic Transaminases)	SMQ	Narrow	"Drug Related Hepatic Disorders"
Gastrointestinal Perforations	SMQ	Narrow	"Gastrointestinal Perforation"
Anemia	CMQ		"Non-Hemolytic and Non-Aplastic Anemias"
Neutropenia	CMQ		"Hematological Toxicity – Neutropenia"
Lymphopenia	CMQ		"Hematological Toxicity – Lymphopenia (Veliparib Product Specific)"
Herpes Zoster	CMQ		"Herpes Zoster"
Creatine Phosphokinase (CPK) Elevation	PT		Search only for the PT of "Blood creatine phosphokinase increased"
Renal Dysfunction	SMQ	Narrow	"Acute Renal, Failure"
Tuberculosis	CMQ		"Tuberculosis"
Adjudicated Cardiovascular Events	Output from CAC		

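### Bleeding is one of three potential ABBV-105 risks named in the protocol but, unlike anemia and lymphopenia, has no AESI category or grouped MedDRA query, so a dose- or combination-related pattern may be missed

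*Protocol*

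**What the plan says.** Protocol section 2.2 lists three potential risks of ABBV-105 suggested by animal studies and ex vivo human samples: "anemia, bleeding associated with platelet dysfunction, and lymphopenia".

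Protocol section 6.1 opens its AESI list with "The following adverse events of special interest (AESI) will be monitored during the study". Of its 14 categories, anemia and lymphopenia are two; none concerns bleeding.

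SAP Appendix B begins "Adverse Events of Special Interest (AESI) will be identified using the following search criteria". Anemia has a company query ("Non-Hemolytic and Non-Aplastic Anemias") and so does lymphopenia. There is no haemorrhage row.

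AESI status brings three outputs:
- a grouped summary by treatment received and overall (SAP 9.2.6);
- an estimated arm difference with an interval (SAP 9.2.2: "For AESIs, the point estimate and 95% CI (using normal approximation) will be provided for the treatment difference in AE percentages");
- a listing of its own (SAP 9.2.11).

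For other events the rule is in SAP 9.2.3: "The number and percentage of subjects experiencing adverse events will be tabulated by SOC and MedDRA PT". Frequent-event, severity and relationship tables, a ranking of preferred terms for the total active group, and the serious-event and discontinuation outputs are also planned.

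**The concern.** The plan treats three risks of the same origin in two different ways, and neither document gives a reason. Anemia and lymphopenia will each appear as one count per arm with an interval for the difference. Bleeding will appear as separate terms.

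Bleeding suits term-by-term reporting poorly. The trial's own toxicity criteria (Protocol Appendix F) place petechiae under dermatologic events, gastrointestinal and rectal bleeding under gastrointestinal events, and haematuria under urinalysis. In arms of 20 to 60 subjects, each term may hold only a few events.

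The main objective is to evaluate safety and to define dose(s) for further development. The trial has three ABBV-105 doses and a combination arm, so it can show whether bleeding rises with dose or with added upadacitinib, provided that the events are counted together. If they are not, a moderate pattern could go unnoticed in the trial that sets the next dose.

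**Working it through.** **Text check**

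| Named risk (Protocol 2.2) | Protocol 6.1 AESI list | SAP Appendix B query | AESI summary, 95% CI, listing |
|---|---|---|---|
| Anemia | yes | yes | yes |
| Lymphopenia | yes | yes | yes |
| Bleeding | no | no | no |

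No other section fills the gap. SAP 9.6 covers ECG only, SAP 10.0 plans nothing further, and Protocol Table 3 has no supplemental bleeding form. The platelet rule in Protocol Table 4 uses the count, whereas the named risk is platelet dysfunction, which a count does not measure.

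**Like-for-like illustration.** The plan states no bleeding figure, so there is none to reproduce. From the documents: 40 subjects per ABBV-105 monotherapy arm (SAP 2.3), and the table of events in more than 5% of an arm (SAP 9.2.10). Since 5% of 40 is 2, a row needs at least 3 subjects to enter. Assumed: 10% of subjects bleed, each under one term, split evenly over four terms, so 10% / 4 = 2.5% per term.

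Expected subjects in one arm of 40:
- Grouped: 40 × 0.10 = 4
- Per term: 40 × 0.025 = 1

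Chance of at least 3 of 40, with X binomial: P(X ≥ 3) = 1 − P(0) − P(1) − P(2).
- Grouped (p = 0.10): 1 − 0.015 − 0.066 − 0.142 = 0.78
- Any given term (p = 0.025): 1 − 0.363 − 0.373 − 0.186 = 0.08
- At least one of the four terms, treated as independent: 1 − (1 − 0.078)^4 = 0.28

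So some bleeding term would enter the table in roughly a quarter of cases, but with only part of the count.

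The same calculation for other assumed rates and numbers of terms:

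| Assumed rate | Grouped | Given term, 3 terms | Given term, 5 terms |
|---|---|---|---|
| 10% | 0.78 | 0.15 | 0.05 |
| 20% | 0.99 | 0.50 | 0.21 |

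**How the SAP's interval behaves when counts are sparse.** Take 4 of 40 on an ABBV-105 dose against 0 of 20 on placebo, a difference of 10%.
- Normal approximation (SAP 9.2.2): SE = √(0.10 × 0.90 / 40 + 0) = 0.0474. The 95% CI is 10% ± 1.96 × 4.74% = 0.7% to 19.3%. The zero cell adds no variance.
- Fisher's exact test on the same counts: two-sided p about 0.29.
- Score-based (Newcombe) interval: the Wilson limits are 4.0% to 23.1% for 4/40 and 0% to 16.1% for 0/20. Lower limit: 10 − √((10 − 4.0)² + (16.1 − 0)²) = −7.2%. Upper limit: 10 + √((23.1 − 10)² + (0 − 0)²) = 23.1%.

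The planned interval excludes zero. The exact test and the score-based interval do not support that conclusion.

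**The case against.** The strongest case against is that the existing outputs show a good deal.
- SAP 9.2.3 tabulates all treatment-emergent events with no frequency threshold and counts a subject once per organ class, which groups events in part.
- It ranks preferred terms for the total active group, so pooled counts per term are planned.
- Its 2% table catches a single subject in an arm of 40 (1/40 = 2.5%) or of 20 (5%). The more-than-5% table used above is the least favourable one.
- Serious bleeds and events leading to discontinuation are tabulated and listed.
- SAP 9.2.2 lets further tabulations be added on the advice of Clinical and Safety, and because events are MedDRA-coded a haemorrhage query can be run at any time.
- The monitoring committee reviews unblinded safety data under a separate charter, which may include bleeding.
- Protocol 2.2 reports good tolerability and no serious events in Phase 1.

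Most of this stands, and it limits the point to aggregate detection and pre-specification. It does not remove it. None of these outputs counts subjects with any bleeding event by arm. The clause in SAP 9.2.2 is discretionary and does not name bleeding, and a grouping chosen after unblinding is weaker evidence than one fixed beforehand. The charter is not available, and committee review does not replace a summary in the final report. The Phase 1 statement concerns healthy adults and does not withdraw the named risk.

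A reader might also infer a much larger effect by pooling: at an assumed 10%, 18 of the 180 subjects given ABBV-105 (60 + 3 × 40), against about 1 of the 60 not given it (40 + 20) at an assumed 2%. The documents do not support setting that beside 1 of 40 for one term in one arm. Most of the jump from 1 to 18 comes from pooling arms, and the SAP plans no exposed-versus-unexposed comparison for any AESI.

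**Conclusion.** The point holds as a cheap improvement. Two of the three named ABBV-105 risks have a grouped, pre-specified safety analysis; bleeding does not. Followed exactly, the plan reports non-serious bleeding only as scattered terms in the general tables.

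Like for like, in one arm of 40, the loss is from about 4 subjects in one row to about 1 subject in each of four rows. The chance of at least 3 subjects falls from about 0.78 for the group to about 0.08 for any given term, or about 0.28 for at least one of the four. These figures rest on an assumed 10% rate and an even four-way split. The direction follows from splitting the events; the size depends on the assumptions.

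Two stronger readings are not supported. Bleeding would not go uncollected or wholly unseen, because the events are recorded and serious bleeds are listed. Nor can it be said that each term will hold only 0 to 2 events, since the documents give no bleeding rate. Whether bleeding was left off deliberately cannot be judged from these documents.

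**What to change.** Add a 'Bleeding events' row to SAP Appendix B, identified by a standard MedDRA haemorrhage query, and add the matching category to the protocol AESI list so that the documents agree. Summarise it by treatment group like the other AESIs: count, percentage, difference with CI, and listing.

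Use an exact or score-based interval where counts are sparse, because the normal approximation in SAP 9.2.2 is unreliable with a zero cell. If a comparison of all subjects given ABBV-105 with all others is wanted, define that pooling in the SAP before unblinding; the new row alone does not create it.

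The cost is one query row and its tables, with no new data, visits or change in clinical management. The downside is one more sparse category to interpret, with wide intervals in arms of 20 to 60.
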